4.1.2.3 GUIDE-HF Single Arm: Descriptive Endpoints

Descriptive endpoints are reported using only summary statistics and no hypothesis tests will be performed. Differences (or ratios) will be provided but no p-values will be generated. Also, the descriptive endpoints will not be used for making claims or changing the labelling. Please see Section 5.2.3 for additional details regarding the analysis of the descriptive endpoints. All mortality and hospitalization-related components of the primary endpoints will be adjudicated by the CEC. The following additional data will be collected and analyzed:

- Health status at baseline, 6, and 12 months post-implantation as assessed by EQ-5D-5L
- Health status at baseline, 6, and 12 months post-implantation as assessed by the KCCQ-12
- 6MHW test at baseline, 6, and 12 months post-implantation
- Cardiovascular mortality at 12 months post-implantation
- All-cause hospitalizations at 12 months post-implantation
- Frequency of subject PAP uploads through 12 months
- Frequency of clinician review of subject PAP uploads through 12 months
- HF medication changes through 12 months
- PAP measurements from baseline through 12 months
- NT-proBNP (or BNP) at baseline, 6 months, and 12 months

5.0 STATISTICAL METHODS

The following section describes the hypotheses and statistical methods for the clinical trial and justification of the design. Hypothesis tests will be 1-sided and conducted at a significance level of 2.5% unless stated otherwise.

5.1 GUIDE-HF Randomized Arm

5.1.1 GUIDE-HF Randomized Arm - Primary Endpoint

5.1.1.1 Hypothesis

To demonstrate effectiveness of PAP-guided HF management compared to standard-of-care-guided HF management, the following hypothesis will be tested:

H_0 : Hazard ratio (HR) for the Composite Endpoint at 12 months (Treatment to Control) ≥ 1

H_1 : HR for the Composite Endpoint at 12 months (Treatment to Control) < 1

In mathematical form, the hypotheses are defined as follows:

$H_0: e^{\beta_1} \geq 1$

$H_1: e^{\beta_1} < 1$

where e is the exponential function and β_1 is the regression coefficient obtained from the covariate representing randomized group (Treatment or Control) [REDACTED]

5.1.1.2 Analysis Methods

[REDACTED]

5.1.1.3 Sample Size

[REDACTED]

[REDACTED]

[REDACTED]

[REDACTED]

[REDACTED]

[REDACTED]

[REDACTED]

[REDACTED]

5.1.1.4 Analysis Population

The analysis population will include subjects randomized to either Treatment or Control group.

5.1.1.5 Poolability Analysis

[REDACTED]

[REDACTED]

Abbott

Study Document No.:

Study Name: CardioMEMS™ GUIDE-HF IDE

Statistical Analysis Plan

5.1.1.6 Sensitivity Analysis

A high-contrast, black and white image showing two large, dark rectangular blocks. The top block is positioned at the top of the frame, and the bottom block is positioned below it, occupying the lower two-thirds of the frame. Both blocks have a slightly irregular, stepped or jagged edge, suggesting a high-resolution scan of a physical object or a specific experimental visualization. The background is a uniform white.

1 [REDACTED]

For more information, contact the Office of the Vice President for Research and Economic Development at [contact] or [contact].

Page 11 of 51

[REDACTED]

[REDACTED]

5.1.1.7 Subgroup Analysis

[REDACTED]

[REDACTED]

[REDACTED]

[REDACTED]

[REDACTED]

[REDACTED]

[REDACTED]

[REDACTED]

[REDACTED]

[REDACTED]

[REDACTED]

[REDACTED]

[REDACTED]

[REDACTED]

[REDACTED]

[REDACTED]

5.1.2 GUIDE-HF Randomized Arm: Secondary Safety and Effectiveness Endpoints

The secondary effectiveness endpoints of the GUIDE-HF Randomized Arm are the composite of HFH and emergency department/hospital outpatient observation visits for intravenous diuretic therapy at 12 months post-implantation (i.e., HFH + HFH Equivalents) as well as health status, as assessed by the EQ-5D-5L Questionnaire and the KCCQ-12, and the 6MHW test at baseline, 6, and 12 months post-implantation. In addition, the individual components of the primary endpoint will each be evaluated as descriptive secondary effectiveness endpoints: HFH at 12 months post-implantation, HFH Equivalents at 12 months post-implantation, and all-cause mortality at 12 months post-implantation.

[REDACTED]

The analysis population for the secondary effectiveness endpoints will include subjects randomized to either Treatment or Control groups.

[REDACTED]

[REDACTED]

The secondary safety endpoint of the GUIDE-HF Randomized Arm is freedom from DSRCs at 12 months post-implantation. The analysis population for the secondary safety endpoint will include subjects enrolled in the Randomized Arm (i.e. with an attempted implant, whether successful or unsuccessful).

5.1.2.1 HFH + HFH Equivalents at 12 months post-implantation

5.1.2.1.1 Hypothesis

To demonstrate effectiveness of PAP-guided HF management compared to standard-of-care-guided HF management with respect to HFH + HFH Equivalents, the following hypothesis will be tested:

H_0 : HR for HFH + HFH Equivalents at 12 months (Treatment to Control) ≥ 1

H_1 : HR for HFH + HFH Equivalents at 12 months (Treatment to Control) < 1

[REDACTED]

[REDACTED]

[REDACTED]

5.1.2.1.2 Analysis Methods

[REDACTED]

5.1.2.1.3 Sample Size

[REDACTED]

5.1.2.1.4 Missing Data Sensitivity Analyses

[REDACTED]

[REDACTED]

[REDACTED]

5.1.2.2 EQ-5D-5L at 6 and 12 Months

5.1.2.2.1 Hypothesis

To demonstrate effectiveness of PAP-guided HF management compared to standard-of-care-guided HF management with respect to the EQ-5D-5L, the following hypothesis will be tested for the EQ-5D-5L visual analogue scale (VAS):

$$H_0: \text{Treatment effect}_{\text{EQ-5D-5L VAS}} \leq 0$$

$$H_1: \text{Treatment effect}_{\text{EQ-5D-5L VAS}} > 0$$

5.1.2.2.2 Analysis Methods

The null hypothesis will be rejected if the [REDACTED] shows benefit of Treatment over Control and the p-value is less than 2.5% using a one-sided test.

5.1.2.2.3 Missing Data

5.1.2.2.4 Sensitivity Analysis

5.1.2.3 KCCQ-12 at 6 and 12 Months

5.1.2.3.1 Hypothesis

[figure not shown]
To demonstrate effectiveness of PAP-guided HF management compared to standard-of-care-guided HF management with respect to the KCCQ-12, the following hypothesis will be tested for the KCCQ-12:

H_0 : Treatment effect_{KCCQ-12 Overall Summary Score} ≤ 0

H_1 : Treatment effect_{KCCQ-12 Overall Summary Score} > 0

5.1.2.3.2 Analysis Methods

The null hypothesis will be rejected if the [REDACTED] show benefit of Treatment over Control and the p-value is less than 2.5% using a one-sided test.

5.1.2.3.3 Missing Data

[REDACTED]

5.1.2.3.4 Sensitivity Analysis

[REDACTED]

5.1.2.4 6MHW test at 6 and 12 Months

5.1.2.4.1 Hypothesis

To demonstrate effectiveness of PAP-guided HF management compared to standard-of-care-guided HF management with respect to the 6MHW test, the following hypothesis will be tested for the 6MHW test:

$$H_0: \text{Treatment effect}_{6\text{MHW}} \leq 0$$

$$H_1: \text{Treatment effect}_{6\text{MHW}} > 0$$

[REDACTED]

[REDACTED]

[REDACTED]

5.1.2.4.2 Analysis Methods

[REDACTED]

[REDACTED]

[REDACTED] The null hypothesis will be rejected if the [REDACTED] show benefit of Treatment over Control and the p-value is less than 2.5% using a one-sided test.

5.1.2.4.3 Missing Data

[REDACTED]

5.1.2.4.4 Sensitivity Analysis

[REDACTED]

5.1.2.5 Individual Components of the Primary Endpoint

The individual components of the primary endpoint will each be evaluated as descriptive secondary effectiveness endpoints:

5.1.2.5.1 HFH at 12 months post-implantation

[REDACTED]

5.1.2.5.2 HFH Equivalents at 12 months post-implantation

[REDACTED]

5.1.2.5.3 All-Cause Mortality at 12 months post-Implantation

[REDACTED]

[REDACTED]
[REDACTED]

5.1.2.6 Secondary Safety Endpoint: Freedom from DSRCs over 12 Months Post-Implantation

The secondary safety endpoint of freedom from DSRCs is defined as an adverse event that is related or possibly related to the system (wireless pressure sensor or external electronics) and has at least one of the following characteristics:

- is treated with invasive means (other than intramuscular medication or a right heart catheterization which is used for diagnostic purposes)
- results in the death of the subject
- results in the explant of the device

The frequency of DSRCs and the frequency and proportion of subjects having freedom from DSRCs at 12 months post-implantation will be reported by group.

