3.1.2 Device Description and Intended Purpose

The CardioMEMS™ HF System is currently indicated for wirelessly measuring PA pressure and heart rate to guide HF management in NYHA Class III HF patients who have been hospitalized for HF in the previous year. The resultant hemodynamic data are used by clinicians for HF management with the goal of reducing HFHs. The CardioMEMS™ HF System received FDA approval for that indication on May 28, 2014. The GUIDE-HF trial will evaluate the use of the CardioMEMS™ HF System for wirelessly measuring PA pressure to guide HF management in NYHA Class II, III, or IV HF patients who have been hospitalized for HF or who have elevated NT-proBNP (or BNP).

The CardioMEMS™ HF System provides PA hemodynamic data to monitor and manage HF patients. The CardioMEMS™ HF System measures PA pressure which clinicians use to initiate or modify HF treatment.

The CardioMEMS™ HF System includes the following components:

- CardioMEMS™ PA Sensor and Delivery Catheter
- CardioMEMS™ Hospital Electronic Unit
- CardioMEMS™ Patient Electronic Unit
- Merlin.net™ (patient database website)

The implantable CardioMEMS™ PA Sensor measures PA pressure using Micro-ElectroMechanical System (MEMS) technology, which enables powering of the implanted sensor via external interrogation thus removing the need for batteries or leads. It is fabricated using silicon wafers and measures 15 mm in length, 3.4 mm in width and 2 mm in thickness.

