4.3.1.2 Secondary Endpoints

The secondary effectiveness endpoints are:

- Composite of recurrent HFHs or emergency department/hospital outpatient observation visits for intravenous diuretic therapy
- Health status at baseline, 6, and 12 months post-implantation as assessed by the EuroQol 5-Dimension, 5-Level (EQ-5D-5L) Questionnaire

- Health status at baseline, 6, and 12 months post-implantation as assessed by the Kansas City Cardiomyopathy Questionnaire (KCCQ-12)
- Six Minute Hall Walk (6MHW) test at baseline, 6, and 12 months post-implantation
- In addition, the individual components of the primary endpoint will each be evaluated as descriptive secondary effectiveness endpoints:
 - HFHs at 12 months post-implantation
 - Emergency department/hospital outpatient observation visits for intravenous diuretic therapy at 12 months post-implantation
 - All-cause mortality at 12 months post-implantation

The secondary safety endpoint is freedom from device/system related complications (DSRCs) at 12 months post-implantation. The secondary safety endpoint will be evaluated for all subjects enrolled in the Randomized Arm (i.e. with an attempted implant, whether successful or unsuccessful) and reported for the entire subject cohort and by subject group.

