4.3.2.2 Secondary Endpoints

The secondary effectiveness endpoints are:

- Composite of recurrent HFHs or emergency department/hospital outpatient observation visits for intravenous diuretic therapy at 12 months post-implantation
- HFHs at 12 months post-implantation compared to HFHs in the 12 months prior to implantation. All subjects who receive a CardioMEMS™ PA Sensor implant will be included in the analysis of this endpoint.
- In addition, the individual components of the primary endpoint will each be evaluated as descriptive secondary effectiveness endpoints:
 - HFHs at 12 months post-implantation

- Emergency department/hospital outpatient observation visits for intravenous diuretic therapy at 12 months post-implantation
- All-cause mortality at 12 months post-implantation

The secondary safety endpoint is freedom from DSRCs at 12 months post-implantation. The secondary safety endpoint will be evaluated for all subjects enrolled in the Single Arm (i.e. with an attempted implant, whether successful or unsuccessful) and reported for the entire subject cohort and by subject group.

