 - An inpatient or prolonged hospitalization OR
 - A medical or surgical intervention to prevent life-threatening illness or injury or permanent impairment to a body structure or a body function OR
 - Fetal distress, fetal death or a congenital abnormality or birth defect

Note: A planned hospitalization for a pre-existing condition, or a procedure required by the CIP is not considered an SAE.

- **Adverse Device Effect (ADE):** An AE related to the use of an investigational medical device. This definition includes AEs resulting from insufficient or inadequate instructions for use, deployment, implantation, installation, or operation, or any malfunction of the investigational medical device. This definition includes any event resulting from the use error or from intentional misuse of the investigational medical device.
- **Serious Adverse Device Effect (SADE):** ADE that has resulted in any of the consequences characteristic of a serious AE.
- **Unanticipated Adverse Device Effect (UADE):** As defined in 21 CFR §812.3, any serious adverse effect on health or safety or any life-threatening problem or death caused by, or associated with, a device, if that effect, problem, or death was not previously identified in nature, severity, or degree of incidence in the CIP or application (including a supplementary plan or application), or any other unanticipated serious problem associated with a device that relates to the rights, safety, or welfare of subjects.
- **Non-AE Device Issue:** any instance when the device fails to perform or does not function properly without an associated an adverse clinical outcome.
- **Device/System Related Complication (DSRC):** An AE that is related or possibly related to the system (CardioMEMS™ PA Sensor or other components of the CardioMEMS™ HF System) and has at least one of the following characteristics:
 - is treated with invasive means (other than intramuscular medication or a right heart catheterization which is used for diagnostic purposes)
 - resulted in the death of the subject
 - resulted in the explant of the device

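### Read literally, the SAP's definition of a device/system related complication could leave delivery-catheter events out of the only named safety endpoint in either arm

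*SAP*

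**What the plan says.** Each arm has one named safety endpoint. For the Randomized Arm, protocol 4.3.1.2 states: "The secondary safety endpoint is freedom from device/system related complications (DSRCs) at 12 months post-implantation". Protocol 4.3.2.2 says the same for the Single Arm: "The secondary safety endpoint is freedom from DSRCs at 12 months post-implantation". Protocol 4.3 sends the reader to Appendix C for the event definitions behind the endpoints.

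Appendix C defines a DSRC as "An AE that is related or possibly related to the system (CardioMEMS™ PA Sensor or other components of the CardioMEMS™ HF System", provided that it was treated invasively (with stated exceptions), caused death or led to explant. Protocol 3.1.2 introduces its list with "The CardioMEMS™ HF System includes the following components". The first entry is "CardioMEMS™ PA Sensor and Delivery Catheter", followed by the Hospital Electronic Unit, the Patient Electronic Unit and Merlin.net.

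SAP 5.1.2.6 keeps the three severity criteria but describes the qualifying event as "related or possibly related to the system (wireless pressure sensor or external electronics". SAP 5.2.2.4 repeats that parenthesis for the Single Arm. SAP 5.1.2 and 5.2.2 define the safety population as enrolled subjects "with an attempted implant, whether successful or unsuccessful".

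**The concern.** One endpoint has two definitions, and the one in the analysis document is narrower. A delivery catheter is neither a wireless pressure sensor nor external electronics. A programmer or adjudicator who follows the SAP text could therefore leave out a complication of the catheter that the protocol counts.

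This matters for three reasons. The endpoint is the only named safety endpoint in both arms. Protocol 6.1.1.3 and 6.2.1.3 say that primary and secondary endpoints will support label claims. And the safety population deliberately includes failed implant attempts, where complications of delivery are to be expected. Protocol 7.1.1 and 7.1.2 list pulmonary artery perforation and vessel perforation among the anticipated events.

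**Working it through.** The plan gives no DSRC figure to reproduce, so the check compares the texts.

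**Step 1: scope by component.** The components come from protocol 3.1.2, the protocol scope from Appendix C and the SAP scope from 5.1.2.6 and 5.2.2.4.

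| Component | Within the Appendix C definition | Named in the SAP parenthesis |
|---|---|---|
| PA Sensor | Yes | Yes |
| Delivery catheter | Yes | No |
| Hospital Electronic Unit | Yes | Yes, as external electronics |
| Patient Electronic Unit | Yes | Yes, as external electronics |
| Merlin.net | Yes | No |

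**Step 2: severity.** Invasive treatment, death and explant appear in both documents with the same exceptions. The definitions differ in component scope only.

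**Step 3: a test event.** Protocol 3.1.2 describes the sensor as tethered to the delivery catheter, released by removing the tether wire, and the catheter then withdrawn. Suppose a vessel is injured by the catheter during withdrawal and repaired invasively. Under Appendix C the event is related to a listed component and is a DSRC. Under the SAP wording it must be tied, at least possibly, to the sensor or the electronics. The sensor has already been released, so that link may fail. If the injury occurs earlier, with the sensor still tethered, an adjudicator could reasonably judge it possibly related to the sensor, and it would count under both texts.

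**Step 4: direction.** Let N be the number of subjects with an attempted implant, D the number with at least one DSRC under Appendix C, and d the number among these whose only DSRCs fall outside the SAP wording, so that 0 ≤ d ≤ D.

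- Freedom from DSRCs, protocol definition: 1 − D/N
- Freedom from DSRCs, SAP definition: 1 − (D − d)/N
- Difference, SAP minus protocol: d/N ≥ 0

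The difference cannot be negative. The SAP wording either leaves the figure unchanged or makes it more favourable.

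**Step 5: size.** The documents give neither D nor d. The planned numbers of successful implants are about 1000 and 2600, and N is at least that large if those targets are met. One reclassified subject would then move the figure by at most about 1/1000 = 0.1 percentage points in the Randomized Arm and 1/2600 = 0.04 percentage points in the Single Arm. These are amounts per subject, not estimates of the effect.

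**Step 6: what depends on it.** SAP 5.7 and protocol 6.1.1.3 and 6.2.1.3 tie the success of each arm to its primary endpoint. The visible DSRC analysis reports frequencies and proportions, with no hypothesis, margin or performance goal. Sample size, power and alpha are the same under either definition.

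**The case against.** The strongest reply is that this is loose wording with no practical effect. The protocol treats sensor and catheter as one item in Table 1 and in the 3.1.2 list, so the SAP's sensor may be shorthand for both. The test of possible relatedness is generous, and the sensor is tethered to the catheter during delivery. The CEC reviews all ADEs, SADEs and UADEs that could contribute to the endpoint, with no exclusion by component (protocol 5.10.4 and 8.2.1), and Appendix C remains the protocol's source of definitions. The ADE definition covers deployment and implantation, and SAP 6.2 summarises ADEs, SADEs and UADEs for enrolled subjects.

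Much of this stands, and it rules out several stronger readings that a reader might infer:

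- *Catheter events certainly drop out.* No SAP sentence excludes them, and many could qualify through possible relation to the sensor.
- *Failed implants are event-free by construction.* Protocol 7.1.2 anticipates failure of the sensor to deploy, so a failed attempt can involve the sensor itself.
- *The understatement can be given as a percentage.* There is no DSRC rate to work from, and any figure would only restate its own assumption. Counting access-site entries in protocol 7.1.2 does not help, because the procedure also uses venous access, a balloon-tipped PA catheter and a guidewire, and minor access-site events need not meet the severity criteria.
- *The randomized comparison is biased.* Both groups are implanted before allocation, so nothing here favours one group.

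What the reply does not do is remove the conflict. The SAP names the sensor without the catheter, does not say that its parenthesis is illustrative, and differs from the document that the CEC would otherwise apply. Adjudication needs one definition. The SAP 6.2 summary keeps the events visible, but it does not apply the DSRC criteria and is not the endpoint.

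**Conclusion.** The mismatch is real and appears in both arms. The SAP definition is narrower than the protocol's and, read literally, could exclude invasively treated or fatal delivery-catheter complications from the only named safety endpoint. Any effect runs towards a more favourable safety figure. Its size cannot be estimated from the documents and may be zero. The events would remain in SAP 6.2, and trial success, power and alpha are untouched. The definition should be corrected, but the conduct or success of the trial is not at risk.

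The conclusion rests on reading the SAP parenthesis as a complete list and the sensor as distinct from the catheter. The CEC charter is not among the documents, and the protocol text under 6.1.2.6 and 6.2.2.4 cannot be seen. Either could already settle the matter.

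**What to change.** In SAP 5.1.2.6 and 5.2.2.4, replace the parenthesis with the Appendix C wording verbatim, so that a DSRC is an event "related or possibly related to the system (CardioMEMS™ PA Sensor or other components of the CardioMEMS™ HF System". Add that the components are those listed in protocol 3.1.2, including the delivery catheter. Referring to that list is safer than writing a new one, which could omit an item such as Merlin.net and create another mismatch. Have the CEC classify DSRCs by this single definition in both arms.

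The cost is SAP wording and a check that the CEC charter agrees. No new data are needed, because the relevant events are already reported and adjudicated. The downside for the sponsor is that the freedom-from-DSRC figure may become slightly less favourable.

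A separate edit belongs in the same paragraph. SAP 5.1.2.6 reports DSRCs by group only, whereas protocol 4.3.1.2 also asks for the entire cohort. Subjects with an unsuccessful implant are not randomized (protocol 5.4.4.1) and have no group, so a whole-cohort row is needed to show them.

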5.1.3 GUIDE-HF Randomized Arm: Descriptive Endpoints

Each of the following descriptive endpoints will be evaluated for the Treatment and Control groups separately and will be descriptively compared: [REDACTED]

population will include subjects randomized into the Treatment and Control groups.

5.1.3.1 Cardiovascular Mortality at 12 Months Post-Implantation

5.1.3.2 All-Cause Hospitalizations at 12 Months Post-Implantation

5.1.3.3 Frequency of Subject PA Pressure Uploads through 12 Months

10. *What is the primary purpose of the following statement?*

5.1.3.4 Frequency of Clinician Review of Subject PAP Uploads through 12 Months

Abbott

Study Document No.: [REDACTED]

Study Name: CardioMEMS™ GUIDE-HF IDE

Statistical Analysis Plan

5.1.3.5 HF Medication Changes through 12 Months

[REDACTED]

